12.2 Site Monitoring

The SVI Site Monitoring Plan will be guided by the FDA Guidance on Risk-Based Monitoring and will be a combination of remote and on-site monitoring. Briefly, the designated monitor(s) will be able to check regulatory documents and certain CRFs remotely and the SDMC will work with each site to develop the best plan (i.e., remote access to medical records or uploading files to WebDCU). In addition to remote monitoring, the monitor(s) will visit the Clinical Centers at specified intervals for the purposes of comparing source documents (such as hospital/clinical charts) to electronic Case Report Forms (CRFs) and database verification. This review will also verify adherence to local regulations for conducting clinical research, protocol eligibility criteria and protocol schedule, and to ensure the consistency, accuracy, and completeness of the data. At all times the monitor will ensure that subject confidentiality is maintained. The investigator agrees that he/she will ensure that any issues, problems, or need for corrections that arise during the conduct of the study will be resolved in a timely manner. Additional details are located in the current version of the SVI Manual of Procedures located in WebDCU™.

12.3 Data Security and Confidentiality

During the course of the trial, user access to the files with subject identifiers, treatment assignment and files with study outcomes will be restricted to core SDMC staff with any exceptions to be approved by the Executive Committee.

In addition to use of passwords and other security measures, all documents containing identifying information on individuals or physicians are considered confidential materials and will be safeguarded to the greatest possible extent. No information, which identifies a specific person, hospital, or physician, will be released to, or discussed with anyone other than study staff members.

Because the SDMC uses a web-based system, source documents and CRFs will remain at the participating sites. The study database only identifies study subjects by unique study identification codes. All data will be stored in a manner that is HIPAA compliant, without the ability to track the information back to a specific subject except through a password protected system. All collected information about a subject will be stored by a unique identification code. All SDMC personnel are certified by the NIH Office of Human Subjects Research in the Protection of Human Research Subjects course.

13.0 STATISTICAL CONSIDERATIONS

13.1 Non-Inferiority Margin

Given the high economic and opportunity costs associated with pancreatic stent placement, as well as the risks of attempted but unsuccessful insertion, we believe that rectal indomethacin would replace PSP in clinical practice if we can demonstrate that it results in less than a 5% greater PEP rate compared to the combination of indomethacin and PSP. The 5% threshold is referred to as the non-inferiority margin.

The value of this margin is based on a combination of statistical reasoning and clinical judgment and was chosen to ensure that the overall PEP proportion of the new treatment (indomethacin

alone) demonstrates a clinically *unimportant* difference from the active comparator arm (the combination of stent and indomethacin) as well as a clinically relevant superiority over a putative placebo (i.e., stent alone).

From a statistical perspective, the margin should retain at least 50% of the superiority of the combination of stent and indomethacin (the active control in the trial) when compared to stent alone.^{20,21} Our recent indomethacin RCT conducted in high-risk patients revealed that the absolute risk difference in the proportion of subjects with post-ERCP pancreatitis between those that received indomethacin plus stent versus those who received stent alone was 6.4% (95%CI: 0.5%, 12.3%) (27). Therefore, taking a fraction of this value gives a non-inferiority margin (δ) of 3.2% ($\delta = .5*6.4$).

Independent to the statistical approach, a questionnaire was circulated to clinical stakeholders regarding how much better (in absolute terms) combination therapy would have to be in preventing PEP as compared to indomethacin alone to justify continuing the use of combination therapy in clinical practice. Seven of 11 respondents said that combination therapy would have to be 10% more effective and the remaining 4 said that it had to be at least 5% more effective.

Based on both the statistical and clinical information, the pre-specified non-inferiority margin was set at 5%. The clinical investigators unanimously judged that a difference in treatment effect of 5% or greater constitutes an important difference between PEP proportions between the two treatment arms indicating that a strategy of indomethacin alone is inappropriate to adopt due to the higher risk of PEP. Although the statistical guidance suggested a lower margin (3.2%), a non-inferiority margin of 3.2% was considered impractical as it would require a sample size of approximately 1700 subjects per arm (to maintain the proposed 85% power), and it was strongly perceived by experts in the field that a margin of 5% would be adequate to definitively impact clinical practice if non-inferiority is declared.

13.2 Sample Size Calculation

The sample size is estimated using a confidence interval approach focusing on the upper confidence limit for a difference in proportions via simulation using nQuery.²³ Based on results of our prior randomized controlled trial, the rate of PEP in subjects receiving the combination of indomethacin and PSP is estimated to be 9.5% for the risk-adjusted population and 9.7% of the unadjusted population.²² We chose to use the higher (unadjusted) proportion for a more conservative approach to sample size estimation. Based on this information, the study is powered to assure 85% likelihood of identifying less than a 5% absolute difference (non-inferiority margin) in PEP rates between the two treatment groups. For sample size estimation for a non-inferiority design, we set the independent proportions to be equal between the two treatment arms, the confidence level for the upper limit at 0.975 (equivalent to a one-sided 2.5% level test) and the upper limit of the confidence interval at 5% (NI margin). The maximum sample size required for randomization is 1300 subjects (650 per treatment group). Due to the potential non-adherence rate, the total sample size is inflated by 5% to account for a small probability of treatment crossovers or losses to follow-up. Thus, a total of 1430 subjects will need to be enrolled and randomized. The sample size was increased to a maximum of 2,180 in order to attain 85% power. This increase was due to the DSMB recommendation based on the review of the planned blinded sample size re-estimation in September 2017.

We recognize that sample size estimation is based on assumptions and if the control (i.e., combination arm) PEP rate is higher than 9.7% then we may begin to see a decrease in power. To reduce the likelihood of an underpowered study due to incorrect sample size assumptions, a blinded sample size re-estimation will be conducted at the time of the first planned futility analysis (but prior to the futility analysis). The study Statistical Analysis Plan (SAP) contains the details of this process.

13.3 Statistical Analyses

An intention-to-treat approach will be the primary basis for analysis. For the analysis of the primary and secondary endpoints, the two-sided 95% upper confidence bound (equivalent to the one-sided 97.5% upper confidence bound) of the observed risk difference in the proportion of patients developing post-ERCP pancreatitis (or moderate-severe PEP) between the two treatment groups (indomethacin alone – combination of indomethacin and PSP) will be calculated. Indomethacin alone will be declared non-inferior to combination therapy if the two-sided 95% upper confidence bound of the treatment difference is less than 5%. If indomethacin is found to be non-inferior, an analysis for superiority will be conducted using a one-sided two sample test for independent binomial proportions.²⁴

Exploratory subgroup analyses will be performed as specified in the Statistical Analysis Plan (SAP). These exploratory subgroup analyses will allow the development of hypotheses about subgroups of patients that may particularly benefit from PSP.

All statistical analyses are outlined in the study Statistical Analysis Plan.

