2.2 Secondary

1. To assess whether rectal indomethacin alone is non-inferior by a pre-specified amount **therapeutic effect** to the combination of rectal indomethacin and PSP for decreasing the severity of PEP in high-risk cases.
2. To establish a repository of whole blood, serum, plasma, urine, duodenal fluid, and stool from study subjects that will allow future translational research elucidating the molecular and genetic mechanisms of PEP, as well as the mechanisms by which non-steroidal anti-inflammatory drugs prevent this complication.

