## 4. NON-INFERIORITY MARGIN AND SAMPLE SIZE DETERMINATION FOR THE PRIMARY OBJECTIVE

### 4.1 Non-inferiority Margin

The non-inferiority margin is set at an absolute margin of 0.05; i.e., indomethacin alone will be considered non-inferior to the combination if it is shown that the upper limit of the two-sided 95% confidence interval of the absolute difference between the two PEP proportions (indomethacin – combination) is less than 5%. The value of this margin is based on a combination of statistical and clinical judgment and was chosen to ensure that the overall PEP proportion of the new treatment (indomethacin alone) demonstrates a clinically unimportant difference from the active comparator arm (the combination of stent and indomethacin) as well as a clinically relevant superiority over a putative placebo (i.e., stent alone). From a statistical perspective, the margin should retain at least 50% of the superiority of the combination of stent and indomethacin (the active control in the trial) when compared to stent alone. Our recent indomethacin RCT revealed that the risk-adjusted proportion of subjects with post-ERCP pancreatitis

in the combination of indomethacin and stent arm was 9.5% and that of stent alone was 15.7%. Unadjusted rates were 9.7% and 16.1%, respectively. Based on these results, the reduction of the combination arm on PEP as compared to stent alone is 6.4%. Therefore, taking a fraction of this value gives a non-inferiority margin ( $\delta$ ) of 3.2% ( $\delta = .5 \times 6.4$ ). This margin is a fraction of the effect of combination compared to stent alone as assessed in the previous trial.

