Independent to the statistical approach, a questionnaire was circulated to clinical stakeholders regarding how much better the combination would have to be in preventing PEP as compared to the indomethacin arm alone to justify continuing the use of the combination therapy. Seven of 11 respondents said 10% more and the remaining 4 said at least 5% more effective. Based on both the statistical and clinical information, the pre-specified margin was set at 5%. The clinical investigators judged that a difference in treatment effect of 5% or greater constitutes an important difference between PEP proportions for the two treatment arms indicating that a strategy of indomethacin alone is inappropriate to adopt due to the higher PEP proportion. Although the statistical guidance suggested a lower margin (3.2%), that small of a margin was considered impractical as it would require a sample size of approximately 1600 per arm if we want to maintain the proposed 85% power. In addition, it should be noted that the determining factor for claiming non-inferiority is the upper limit of a 95% confidence interval. If the rate in the PSP+RI arm is truly 9.7%, then the rate in the RI arm cannot be higher than 11.4% in order to claim non-inferiority as the two-sided 95% confidence interval for this difference is (-1.4%, 4.9%), assuming a sample size of 715 per arm. Assuming 1090 per arm, the rate in the RI arm cannot be higher than 12.0% (95% CI: -0.3%, 4.9%). Reducing the margin lower than 5% would have little gain on the clinical interpretation of the results and would result in an impractical increase in the sample size. As an example, assume a margin of 3% and a PSP+RI PEP rate of 9.7%, the trial would need 1700 per arm to show non-inferiority which would translate into an RI PEP rate of 10.6% and a confidence interval of -1.1%, 2.9%.

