**9.3 Secondary Outcome Variable Analysis**

Analysis of the secondary outcome, the proportion of subjects with moderate-severe PEP, will be analyzed in a similar manner as the primary outcome.

We also will examine the impact of pre-specified characteristics on the primary and secondary outcomes. Specifically, the goal of this analysis is to examine prognostic variables and their impact on the primary analysis. We also will explore subgroup populations for future hypothesis generation. The baseline variables that will be examined are: age (continuous), gender, race, body mass index (continuous), suspicion of sphincter of Oddi dysfunction, prior post-ERCP pancreatitis, history of recurrent pancreatitis, manometrically documented sphincter of Oddi dysfunction, difficult cannulation, pre-cut (access) sphincterotomy, pancreatic sphincterotomy, pancreatic acinarization, biliary sphincterotomy, pancreatic stent placement, double wire technique, make/model/length/caliber of pancreatic stent, trainee involvement, prophylactic stent characteristics, type of sphincter of Oddi dysfunction, and inpatient vs. outpatient status. The assessment of each of these variables will be conducted using a logistic regression model with the dichotomous primary outcome, PEP event. Treatment arm will be a main effect in the model and the above covariates examined. Each covariate will be assessed individually first with a model that includes interaction effect with the treatment. If a significant interaction is observed ( $p < 0.10$ ), then exploratory subgroup analyses will be considered. For each model, we will be looking at the parameter estimate of the covariate to examine its association with outcome. We also will be examining the parameter estimate of the treatment in the presence of the covariate. A multivariable model will be created based on the results of the individual models (a combination of statistical and clinical significance will be used for model inclusion). The final multivariable model will be based on goodness of fit criteria. For this final model, the adjusted risk difference will be estimated with a 95% confidence interval. If the upper limit of this confidence interval is 5% or greater, then non-inferiority of the treatments cannot be concluded in the presence of the particular covariates. This analysis will be run on both the ITT and PP analysis populations.

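### The 5-point margin is justified only for all PEP; for moderate-severe PEP it is either applied without a rationale or not stated at all

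*Protocol*

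**What the plan says.** Protocol 2.2 makes non-inferiority by an amount fixed in advance its first secondary objective, "for decreasing the severity of PEP in high-risk cases". Protocol 11.2 and SAP 3.2 define the matching endpoint as moderate-severe PEP, a subset of the primary endpoint.

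Protocol 13.3 covers both endpoints in one paragraph. It begins "For the analysis of the primary and secondary endpoints, the two-sided 95% upper confidence bound", mentions moderate-severe PEP in parentheses, and continues: "Indomethacin alone will be declared non-inferior to combination therapy if the two-sided 95% upper confidence bound of the treatment difference is less than 5" percent. That rule is not restricted to either endpoint.

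SAP 9.3 says that the secondary outcome, "the proportion of subjects with moderate-severe PEP, will be analyzed in a similar manner as the primary outcome". It gives no other margin.

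The margin is argued in two places:

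- **Protocol 13.1** gives an adoption argument about the PEP rate, half of the 6.4-point prior effect on PEP (3.2 points), and the investigators' judgement about PEP proportions. It also reports a questionnaire on how much better "combination therapy would have to be in preventing PEP as compared to indomethacin alone".
- **SAP 4** is headed "NON-INFERIORITY MARGIN AND SAMPLE SIZE DETERMINATION FOR THE PRIMARY OBJECTIVE". SAP 4.1 states the rule for the "confidence interval of the absolute difference between the two PEP proportions".

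**The concern.** A non-inferiority margin is a judgement about how much excess of one particular outcome is acceptable. A 5-point excess of any PEP, against an expected 9.7%, is one judgement. A 5-point excess of moderate or severe PEP is another: that outcome is rarer and clinically worse, and the documents do not discuss it.

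Read as written, Protocol 13.3 carries the first judgement over to the second outcome without comment. At stake is any statement in the final report that dropping the stent is non-inferior on severity. For an endpoint with a low control rate, that statement could be made after a large relative increase.

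**Working it through.** **Step 1: where the margin applies.** There are two readings, and each leaves a gap.

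| Reading | Support | What is missing |
|---|---|---|
| 5 points governs both endpoints | Protocol 13.3 names both and gives one rule; SAP 9.3 treats the secondary like the primary | A rationale, expected rate and power for moderate-severe PEP |
| 5 points governs the primary only | SAP 4 heading; SAP 4.1 refers to PEP proportions; SAP 3.2 says the design tests the primary hypothesis | Any value for the amount that Protocol 2.2 says is fixed in advance |

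This step uses no assumed rates.

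**Step 2: reproduce the SAP's own figure.** Inputs: 1090 per arm (Protocol 1.0, SAP 4.1), margin 5 points, and the interval in SAP 4.2:

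pI − pC ± 1.96 × √[(pI(1 − pI) + pC(1 − pC))/1090]

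SAP 4.1 states: "Assuming 1090 per arm, the rate in the RI arm cannot be higher than 12.0% (95% CI: -0.3%, 4.9" percent). With pI = 0.120 and pC = 0.097, the standard error is 0.01331 and the interval is 0.023 ± 0.0261, or −0.3% to 4.9%. This agrees. Setting the upper limit to exactly 5% gives pI = 12.1%, which is 12.1/9.7 = 1.25 times the control rate.

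**Step 3: the same rule on a rarer endpoint.** The documents give no moderate-severe rate, so control rates of 2 to 6% are assumed. These are 2/9.7 = 21% to 6/9.7 = 62% of a 9.7% PEP rate. The nearest anchor is Protocol 3.1, which says 12% of PEP runs a severe course. If that share carried over, severe PEP alone would be 0.12 × 9.7 = 1.2%, a floor for moderate-severe PEP.

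For each pC, solve for the pI at which the upper limit equals 5%. Then take a true doubling (pI = 2pC) and find the probability that the upper limit falls below 5%, by exact enumeration of the two binomials.

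| Control rate | Margin ÷ control rate | Worst passing rate, indomethacin alone | Ratio | P(declared non-inferior), true doubling |
|---|---|---|---|---|
| 9.7% (all PEP) | 0.52 | 12.1% | 1.25 | below 0.1% |
| 2% | 2.5 | 5.4% | 2.7 | 98% |
| 3% | 1.7 | 6.2% | 2.1 | 62% |
| 4% | 1.25 | 7.1% | 1.8 | 17% |
| 5% | 1.0 | 7.9% | 1.6 | 3% |
| 6% | 0.83 | 8.8% | 1.5 | 0.3% |

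As a check on one row by normal approximation: at pC = 3% and pI = 6%, the standard error is 0.00886, (0.05 − 0.03)/0.00886 − 1.96 = 0.30, and Φ(0.30) = 62%.

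**Step 4: effect of other conditions.** The last column takes the secondary endpoint alone. If a severity claim were made only when the primary also passes, the chance cannot exceed the chance that the primary passes. With overall control PEP at 9.7%, mild PEP unchanged and moderate-severe PEP doubled, that is 62%, 32%, 11%, 2.5% and 0.4% at control rates of 2, 3, 4, 5 and 6%. Requiring the per protocol sample to agree, as SAP 9.1 does for the primary, would lower the figures further. Neither Protocol 13.3 nor SAP 9.3 makes the secondary declaration conditional on the primary.

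**The case against.** The primary-only reading has real support, set out in step 1, and Protocol 13.3 defers to the SAP for detail. The Protocol 1.0 summary also lists only the biorepository as a secondary objective. On that reading there is no misapplied margin. This stands as far as it goes, but Protocol 2.2 is then left without its number. Conversely, if 13.3 does supply the number, what remains is a missing rationale rather than a missing margin.

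The sizes depend on assumed control rates and an assumed doubling, and they fall quickly: near 5 to 6% a doubling would rarely pass. That also stands. The gap in specification does not depend on those figures; the degree of looseness does.

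A reader might infer two stronger points, and the documents support neither:

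- **That SAP 4.1 vets the margin by showing that the worst passing interval includes zero, and that this safeguard fails for a rarer endpoint.** SAP 4.1 makes no such check. It says the upper limit decides, and it uses the interval to show the largest rate that can pass.
- **That declaring non-inferiority while the interval lies wholly above zero would itself be an error.** Any non-inferiority rule allows it: the treatment is worse, but by less than the margin. It matters only if an excess of that size is unacceptable for this endpoint, which is the judgement the documents leave unmade.

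Finally, the harm is contained. The reported interval would show any excess, SAP 10 compares serious adverse events between arms, and the DSMB monitors safety.

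**Conclusion.** The concern holds as a gap in justification and specification for the secondary endpoint. Protocol 13.3 with SAP 9.3 most naturally applies 5 points to moderate-severe PEP, for which no rationale, expected rate or power is given. The alternative reading leaves the severity objective without a margin.

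Under assumed control rates of 2 to 6% at 1090 per arm, the rule would pass results of about 2.7 down to 1.5 times the control rate, against 1.25 times for all PEP at 9.7%. A true doubling would be declared non-inferior with probability from about 98% at 2% to 0.3% at 6%, before any requirement that the primary or per protocol analysis also pass.

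It would be wrong to infer that the trial's main result is in doubt: the primary conclusion, its power and its sample size are unaffected. The change should be made, but the error is confined to the secondary declaration.

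**What to change.** 1. **Protocol 13.3:** limit the declaration based on the 5% bound to the primary endpoint.
2. **SAP 9.3:** replace the sentence on analysing the secondary outcome like the primary with wording such as: *For moderate-severe PEP the risk difference will be reported with its two-sided 95% confidence interval in the ITT and per protocol samples, without a non-inferiority declaration.* The exception is a separate margin for this endpoint, justified before unblinding on grounds outside this trial's data and stated with its expected rate and power.
3. **Protocol 2.2, first objective:** match the choice, either by naming that margin or by wording the objective as estimation. The severity objective itself stays.

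The cost is text in three places and no new data. Protocol 14.2.2 requires prior Executive Committee and NIDDK approval, DSMB review if the change is substantive, and IRB/REB approval.

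The downside is that the formal secondary non-inferiority claim is given up, or has less power at a smaller margin. As an illustration only, not a proposal, a 2-point margin with equal true rates of 3, 4 or 5% has power Φ(0.02/SE − 1.96). With SE = 0.00731, 0.00839 and 0.00934 at 1090 per arm, that is 78%, 66% and 57%.

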13.4 Interim Analysis

Two interim analyses for futility using conditional power will be conducted when approximately one-third (N~472) of the original sample size and one-half (N~1090) of the revised sample size (N=2180) have been evaluated for the primary outcome and all of the outcomes to be used in the analysis are adjudicated. The goal of the interim analysis plan is to determine whether to stop the trial early because it is unlikely to show non-inferiority at the final analysis. A conditional power will be calculated to assess the probability of observing non-inferiority at the final analysis conditional on the observed data and assumptions on the PEP event rates for the remainder of the trial. Conditional power will be calculated under two different assumptions: 1) the assumption that the PEP rates in the two treatment arms for the remainder of the trial will be the same as those hypothesized (pC=9.7%; pI=9.7%); and, 2) the assumption that the PEP rates observed at the interim analysis will be maintained for the remainder of the trial. See the Statistical Analysis Plan for more details.

